3.1 Objectives and endpoints

Trial objectives and endpoints are listed in [Table 3-1](#).

Table 3-1: Objectives and endpoints of the clinical trial

OBJECTIVES	ENDPOINTS
PRIMARY OBJECTIVE	PRIMARY ENDPOINTS

 (Part 1 and Part 2) Assess safety and tolerability profile of W_pro1 monotherapy or in combination with cemiplimab 	
 Occurrence of dose-limiting toxicities (DLTs). Occurrence of treatment-emergent adverse events (TEAEs) reported by relationship, grade, and seriousness according to NCI CTCAE v5.0.

OBJECTIVES	ENDPOINTS

 (Part 2 Arms 1a and 1b) Evaluate preliminary anti-tumor activity of W_pro1 monotherapy and in combination with cemiplimab in patients with mCRPC based on ORR 	
 Objective response rate (ORR), defined as the number of patients with a complete response (CR) or partial response (PR) per Prostate Cancer Working Group 3 (PCWG3) [3] as determined by the investigator as best objective response divided by the number of patients in the analysis set.
SECONDARY OBJECTIVES	SECONDARY ENDPOINTS

 Evaluate anti-tumor activity based on levels of prostate-specific antigen (PSA) 	
 Prostate-specific antigen (PSA) decline of 0 to 25%, >25% to 50%, and >50% compared to baseline. PSA doubling time (PSADT) post-treatment on C4D1 and D1 of every fourth subsequent cycle (e.g., Cycle 8 Day 1 [C8D1], C12D1, etc.) in Part 1 and Part 2 Arms 1A and 1B, or on C4D1, C8D1, and end of treatment (EoT) in Part 2 Arms 2 and 3 compared to baseline. PSA decline of ≥50% (according to the PCWG3).

 (Part 1) Evaluate preliminary anti-tumor activity of W_pro1 monotherapy in patients with mCRPC based on ORR 	
 ORR, defined as the number of patients with a CR or PR per PCWG3 as determined by the investigator as best objective response divided by the number of patients in the analysis set.

 Evaluate preliminary anti-tumor activity of W_pro1 monotherapy or in combination with cemiplimab in patients with newly diagnosed LPC 	
 Tumor response post-treatment compared to baseline.
EXPLORATORY OBJECTIVES	EXPLORATORY ENDPOINTS

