7 ANALYSIS SETS AND SUBGROUPS

7.1 Analysis sets

The following analysis sets are defined:

Population	Description
Screened	The screened analysis set is defined as all patients who sign the informed consent form (ICF).
Intent-to-Treat (ITT)	Part 1: The ITT set is defined as all patients to whom IMP is assigned. Part 2: The ITT set is defined as all patients who are randomized to the IMP.
Modified Intent-to-Treat (mITT)	Part 1: The mITT set is defined as all patients to whom IMP is assigned and have a baseline and at least one post-baseline (i.e., one on-treatment or post-treatment) tumor assessment (clinical or imaging assessment). Part 2: The mITT set is defined as all patients who are randomized to the IMP and have a baseline and at least one post-baseline (i.e., one on-treatment or post-treatment) tumor assessment (clinical or imaging assessment).
Safety (SAF)	The safety set is defined as all patients who have received IMP (i.e., at least 1 dose of W_pro1 and/or cemiplimab).
DLT Evaluation	Only applicable for Part 1: The DLT evaluation set includes all patients from the safety set who either have completed the DLT evaluation period and meet the minimum exposure criterion or have experienced a DLT during C1. Patients who do not experience any DLTs during C1 are considered to be evaluable if they have been observed for a minimum of 21 days following the first dose and are considered to have sufficient safety data to conclude that a DLT did not occur. A patient is considered to have met the minimum exposure criterion if the relative dose intensity of W_pro1 in C1 is at least 90%.
Per Protocol (PP)	The per protocol (PP) set is defined as all patients who have received IMP and fulfil the following criteria: 
 • The absence of any important protocol deviations that could affect the primary efficacy analysis • The completion of a minimal exposure to the treatment of 1 cycle • Availability of baseline and at least one on-treatment / post-treatment tumor assessment Important deviations will lead to an exclusion of patients from the PP set and will be agreed at the data review meeting (DRM) prior to database snapshot for the final analysis. Protocol deviations that may be considered important will be specified in the SAP (see Section 7.2)

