Pharmacodynamic	The pharmacodynamic set is defined as all patients who have received IMP (i.e., at least 1 dose of W_pro1 and/or cemiplimab) and with a baseline and at least 1 on-treatment/post-treatment follow-up

Population	Description
	pharmacodynamic assessment as specified in Section 8.8.1 (i.e. Hormones (Testosterone), Cytokines).
Subsequent Cemiplimab Monotherapy on Progression (Cemi Mono on PD)	Only applicable for Part 2 Arm 1B: The subsequent cemiplimab monotherapy on progression set (Cemi Mono on PD) is defined as all mCRPC patients in Arm 1B (W_pro1 monotherapy) who switch to cemiplimab monotherapy after disease progression and who received at least one dose of cemiplimab.

The DLT evaluation set will be used for the evaluation of DLTs in order to assess the REDR in Part 1 of the trial.

The safety set will be used for all other safety analyses, while the mITT set will be used as primary analysis set for efficacy analyses.

The subsequent cemiplimab monotherapy on progression set will be used for all exploratory safety and efficacy analyses for the Arm 1B patients who received cemiplimab (i.e., at least 1 dose of cemiplimab) after progression to W_pro1 monotherapy.

The ITT analysis set will be used for disposition analyses.

Further, the ITT and PP sets will be used for sensitivity analyses of some predefined efficacy endpoints depending on the number of patients excluded. If none of the patients are excluded from the mITT set, compared to the ITT set, or if the number of patients excluded from the PP set is small (exclusion rate $\leq 10\%$), no additional sensitivity analyses for the ITT or the PP set will be generated. The final decision to perform sensitivity analyses for the ITT set or for the PP set will be made during the DRM meeting for the final analysis.

All safety analyses and analyses based on the Pharmacodynamic set will be based on the treatment actually taken by the patient (“as treated”).

All other analyses will be based on the treatment the patient was assigned/randomized to (“as randomized”), unless stated otherwise.

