	14.3.1.27	Number (%) of patients with TEAEs leading to permanent discontinuation of W_pro1 by system organ class and preferred term	Safety set	Yes
	14.3.1.28	Number (%) of patients with TEAEs leading to permanent discontinuation of Cemiplimab by system organ class and preferred term	Safety set	Yes
	14.3.1.29	Number (%) of patients with DLTs by system organ class and preferred term	Safety set	Yes
	14.3.1.30	Number (%) of patients with most frequent TEAEs ($\geq 5\%$) by preferred term	Safety set	Yes
	14.3.1.30.1	Number (%) of patients with most frequent TEAEs ($\geq 5\%$) related to IMP by preferred term	Safety set	
	14.3.1.30.2	Number (%) of patients with most frequent TEAEs ($\geq 5\%$) related to W_pro1 by preferred term	Safety set	
	14.3.1.30.3	Number (%) of patients with most frequent TEAEs ($\geq 5\%$) related to Cemiplimab by preferred term	Safety set	
	14.3.1.31	Number (%) of patients with TEAEs by system organ class, preferred term and worst IMP relationship	Safety set	
	14.3.1.32	Number (%) of patients with TEAEs by system organ class, preferred term and worst relationship to W_pro1	Safety set	
	14.3.1.33	Number (%) of patients with TEAEs by system organ class, preferred term and worst relationship to Cemiplimab	Safety set	
	14.3.1.34	Number (%) of patients with TEAEs by system organ class, preferred term and worst NCI CTAE grade	Safety set	
	14.3.1.35	Number (%) of patients with TEAEs related to IMP by system organ class, preferred term and worst NCI CTAE grade	Safety set	
	14.3.1.36	Number (%) of patients with TEAEs related to W_pro1 by system organ class, preferred term and worst NCI CTAE grade	Safety set	
	14.3.1.37	Number (%) of patients with TEAEs related to Cemiplimab by system organ class, preferred term and worst NCI CTAE grade	Safety set	

Header	Table Number	Name	Analysis Set	Interim Analysis
	14.3.1.38	Number (%) of patients with non-serious TEAEs (>3% at preferred term level) by system organ class and preferred term	Safety set	
	14.3.1.39	Number (%) of patients with TEAEs leading to IMP dose modification by system organ class and preferred term	Safety set	
	14.3.1.40	Number (%) of patients with TEAEs leading to W_pro1 dose modification by system organ class and preferred term	Safety set	
	14.3.1.41	Number (%) of patients with TEAEs leading to Cemiplimab dose modification by system organ class and preferred term	Safety set	
		Cemiplimab TEAEs		
	14.3.1.42	Summary of cemiplimab TEAEs	Cemi Mono on PD set	

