	14.3.1.43	Number (%) of patients with cemiplimab TEAEs by system organ class and preferred term	Cemi Mono on PD set	
	14.3.1.44	Number (%) of patients with cemiplimab TEAEs related to Cemiplimab by system organ class and preferred term	Cemi Mono on PD set	
	14.3.1.45	Number (%) of patients with grade ≥ 3 cemiplimab TEAEs by system organ class and preferred term	Cemi Mono on PD set	
	14.3.1.46	Number (%) of patients with grade ≥ 3 cemiplimab TEAEs related to Cemiplimab by system organ class and preferred term	Cemi Mono on PD set	
	14.3.1.47	Number (%) of patients with serious cemiplimab TEAEs by system organ class and preferred term	Cemi Mono on PD set	
	14.3.1.48	Number (%) of patients with serious cemiplimab TEAEs related to Cemiplimab by system organ class and preferred term	Cemi Mono on PD set	
	14.3.1.49	Number (%) of patients with serious cemiplimab TEAEs leading to death by system organ class and preferred term	Cemi Mono on PD set	
	14.3.1.50	Number (%) of patients with serious cemiplimab TEAEs leading to death related to Cemiplimab by system organ class and preferred term	Cemi Mono on PD set	
	14.3.1.51	Number (%) of patients with cemiplimab TEAEs leading to Cemiplimab dose reduction by system organ class and preferred term	Cemi Mono on PD set	
	14.3.1.52	Number (%) of patients with cemiplimab TEAEs leading to Cemiplimab dose delay by system organ class and preferred term	Cemi Mono on PD set	
	14.3.1.53	Number (%) of patients with cemiplimab TEAEs leading to Cemiplimab dose modification by system organ class and preferred term	Cemi Mono on PD set	

Header	Table Number	Name	Analysis Set	Interim Analysis
	14.3.1.54	Number (%) of patients with cemiplimab TEAEs leading to permanent discontinuation of cemiplimab by system organ class and preferred term	Cemi Mono on PD set	
14.3.2		Listings of Deaths, Other Serious and Certain Other Significant Adverse Events	Safety set	
	14.3.2.1	Deaths, Listing	Safety set	Yes
	14.3.2.2	Serious Adverse Events, Listing	Safety set	Yes
	14.3.2.3	Treatment emergent Adverse Events leading to permanent discontinuation of IMP, Listing	Safety set	Yes
	14.3.2.4	Dose-limiting toxicities (Part 1), Listing	Safety set	

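### The DLT percentage, a primary endpoint, is planned on the Safety set, although SAP 7.1 assigns DLT evaluation to a DLT evaluation set that no planned output uses

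*SAP*

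**What the plan says.** SAP 3.1 and protocol section 3 make the occurrence of DLTs a primary endpoint. SAP 7.1 then divides the safety work between two sets: "The DLT evaluation set will be used for the evaluation of DLTs in order to assess the REDR in Part 1 of the trial", and "The safety set will be used for all other safety analyses". Protocol 9.3 gives the same rule.

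SAP 7.1 defines the first set in two limbs. The main limb is this: "The DLT evaluation set includes all patients from the safety set who either have completed the DLT evaluation period and meet the minimum exposure criterion". Patients who fail that limb can still enter the set by the second one, "or have experienced a DLT during C1". The exposure criterion is a relative dose intensity (RDI) of at least 90% in Cycle 1 (C1).

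The output list in SAP 11.1.1 does not carry this through:

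- Table 14.3.1.29, "Number (%) of patients with DLTs by system organ class and preferred term", is assigned to the Safety set.
- Table 14.3.1.1, the adverse event summary, is assigned to the Safety set. SAP 8.9.3 adds a DLT row to it for Part 1.
- Listing 14.3.2.4, "Dose-limiting toxicities (Part 1), Listing", is assigned to the Safety set.
- No row in Section 11 names the DLT evaluation set as its analysis set.

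SAP 8.9.1 promises the number and percentage of Part 1 patients with a DLT but names no set.

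**The concern.** The set named in Section 11 fixes the denominator: SAP 10.2.5.2 bases percentages on patients in the analysis set unless noted otherwise. A programmer working from the list would divide by the Safety set.

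Protocol 4.1.1 expects that some patients will not be evaluable. These are patients who do not complete the DLT window, or who receive fewer than three doses in C1, for a reason other than a DLT. They may be replaced, but having been dosed they stay in the Safety set. In Table 14.3.1.29 they would count as patients observed without a DLT, although the plan's own definition says their data cannot support that. What is at stake is the reported percentage for a primary endpoint in a group of at most 9 patients, where each patient in the denominator shows.

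**Working it through.** The plan states no DLT rate, so there is no figure to reproduce. The check concerns how the two sets are related and what that does to a percentage.

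**Step 1. Relation of the sets.** Let S be the number in the Safety set for Part 1, E the number in the DLT evaluation set, and x the number of patients with a DLT in C1. By definition the DLT evaluation set is part of the Safety set and keeps every patient with a DLT in C1. So x is the same in both sets and E ≤ S, which gives x/S ≤ x/E. The two are equal if E = S or x = 0.

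**Step 2. Size.** S = 9, the number dosed in Part 1 (protocol 2.3 and 4.4). The documents give neither E nor x, so E = 6 to 9 and x = 1 or 2 are assumptions.

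| DLTs in C1 | Safety set, S = 9 | E = 9 | E = 8 | E = 7 | E = 6 |
|---|---|---|---|---|---|
| 1 | 1/9 = 11.1% | 11.1% | 1/8 = 12.5% | 1/7 = 14.3% | 1/6 = 16.7% |
| 2 | 2/9 = 22.2% | 22.2% | 2/8 = 25.0% | 2/7 = 28.6% | 2/6 = 33.3% |

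With x = 0 the percentage is 0 on either set.

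**Step 3. Is a non-evaluable patient plausible?** Take a patient who receives all three C1 doses in full, the third of them d days late. The dose index is then 1, so RDI equals planned over actual treatment duration. Applying the duration formula of SAP 8.9.2 to C1 alone:

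RDI = 21 / (14 + d + 1 + 7) = 21 / (22 + d)

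- d = 0: 21/22 = 95.5%
- d = 1: 21/23 = 91.3%
- d = 2: 21/24 = 87.5%, below the 90% threshold

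Protocol 9.4.5 has the same formula without the extra day. RDI is then 21/(21 + d), and it first falls below 90% at d = 3 (21/24 = 87.5%). Protocol 6.6.1.2 allows dosing to be delayed by up to 21 days to manage adverse events. A patient can therefore be fully dosed, have no DLT, and still fall outside the set.

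**Step 4. Does the numerator always agree?** It does for DLTs in C1, but not beyond. Under protocol 4.1.1 and 6.6.1.1, a patient whose titration is held at a dose level has his DLT assessment period extended to 28 days, while a cycle is 21 days. The set guarantees a place only for a DLT during C1. A patient with a DLT on days 22 to 28 must instead qualify through the exposure criterion. Because his dose was held, his C1 dose is below plan and his RDI may be under 90%; the doses are redacted, so this cannot be computed. Read literally, the definition would then exclude him. If he had the only DLT and the other 8 patients were evaluable (assumptions), the Safety set gives 1/9 = 11.1% and the DLT evaluation set gives 0/8 = 0%.

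**The case against.** The strongest reply is that the Safety set is a deliberate choice. SAP 7.1 ties the DLT evaluation set to assessing the REDR. SAP 8.9 names DLTs in Part 1 among the safety data and makes the Safety set the default unless something else is stated. Protocol 9.4.2 presents the DLT percentage for patients enrolled into Part 1. On this reading Table 14.3.1.29 is a descriptive display and the DLT evaluation set served the dose decision only.

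This has force: the texts pull in two directions, so the table departs from one rule while following another. It does not settle the matter. SAP 7.1 does state something else for DLTs, and on the descriptive reading the SAP defines a set on which it never runs an output. Review material for the Safety Review Committee (SRC) is outside the SAP (SAP section 5), so it does not fill that gap.

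It can also be said that the outputs are easy to correct. SAP section 11 calls its list tentative and does not treat changes to it as deviations, the mock tables are a separate document not available here, and SAP 10.2.5.2 asks for care over denominators. SAP 8.5 also plans a count of patients in each analysis set, so a reader could probably recompute the rate. All this lowers the cost of the fix but leaves open which percentage is the primary-endpoint result.

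A reader might infer that the listing is wrong too. The documents do not support that: a listing has no denominator, and SAP 8.9 puts all safety listings on the Safety set.

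**Conclusion.** The inconsistency is real: SAP 7.1 and the output list give different sets for the DLT percentage, and SAP 8.9.1 does not decide between them. For DLTs in C1 the Safety-set figure can only be equal to or lower than the figure on the DLT evaluation set. With 9 dosed and an assumed 6 to 8 evaluable, one DLT reads 11.1% instead of 12.5% to 16.7%, and two read 22.2% instead of 25.0% to 33.3%.

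Three stronger readings are tempting and are not supported:

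- **That the rate is always lowered.** There is no effect if all 9 are evaluable or if no DLT occurred, and the documents do not say whether either holds. For a DLT after C1 in the extended window, the direction can reverse (step 4).
- **That the Safety set is plainly the wrong denominator.** SAP 8.9 and protocol 9.4.2 give it some support. The two rules need reconciling.
- **That dose selection is affected.** The REDR rules in protocol 4.1.1 count DLTs among evaluable patients, and the SRC reviewed Part 1 on 17 May 2021. No hypothesis test or stopping rule uses this table.

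This is a reporting point on a primary endpoint. It should be corrected before the final analysis.

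**What to change.** 1. Present the DLT number and percentage in Table 14.3.1.29, and in the Part 1 DLT row of Table 14.3.1.1, on the DLT evaluation set, with the Safety-set denominator alongside.
2. Name the DLT evaluation set in SAP 8.9.1 as the set for the DLT percentage.
3. Align the set definition in SAP 7.1 with the assessment period of protocol 4.1.1 and 6.6.1.1, so that a DLT at any time in the patient's own window, including the extended 28 days, secures inclusion. Without this, changing the set alone could drop a late DLT from the primary table.
4. Leave Listing 14.3.2.4 on the Safety set and add a flag for DLT-evaluable patients.

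The cost is one sentence in SAP 8.9.1, one clause in SAP 7.1, a second denominator in two tables and a flag in one listing. No new data are needed. Table 14.3.1.29 is also marked for the interim analysis, which has been run, so a Safety-set version may already exist; showing both denominators lets the two outputs be reconciled.

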11.1.2 Listings

Header	Listing Number	Name	Analysis Set	Interim Analysis
16.2		Patient Data Listings		
16.2.1		Patient Disposition		
	16.2.1.1	Patient disposition	Screened set	Yes
	16.2.1.2	Informed consent	Screened set	
	16.2.1.3	Patients impacted by COVID-19 related study disruption	ITT set	
	16.2.1.4	Missing visits due to COVID-19	ITT set	
16.2.2		Protocol Deviations		
	16.2.2.1	Protocol Deviations	ITT set	
	16.2.2.2	Protocol Deviation due to COVID-19	ITT set	
16.2.3		Patients Excluded from the Efficacy Analysis		
	16.2.3.1	Inclusion/exclusion criteria not met	Screened set	
	16.2.3.2	Exclusion from analysis set	Screened set	Yes
16.2.4		Demographic Data		
	16.2.4.1	Demographics	ITT set	Yes
	16.2.4.2	Disease characteristics	ITT set	Yes
	16.2.4.3	Medical History	ITT set	
	16.2.4.4	Prior systemic cancer therapies	ITT set	Yes
	16.2.4.5	Prior cancer radiotherapies	ITT set	
	16.2.4.6	Prior cancer surgeries	ITT set	
	16.2.4.7	Prior and concomitant medications	ITT set	
	16.2.4.8	Further antineoplastic therapies	ITT set	
	16.2.4.9	Cancer radiotherapies	ITT set	
	16.2.4.10	Procedures and non-drug therapies	ITT set	
16.2.5		Compliance and/or Drug Concentration Data (if available) (Note; exposure information will be included in this section)		
	16.2.5.1	Trial treatment – W_pro1	Safety set	
	16.2.5.2	Trial treatment – Cemiplimab	Safety set	
	16.2.5.3	Trial treatment – ADT	Safety set	
	16.2.5.4	Drug exposure	Safety set	Yes
16.2.6		Individual Efficacy Response Data		
		Primary and Secondary Efficacy Endpoint		
	16.2.6.1.1	Overall PCWG3 and LPC tumor response assessment based on Radiological Soft Tissue Evaluation per Investigator	ITT set	Yes
	16.2.6.1.2	PCWG3 and LPC tumor assessment based on Radiological Soft Tissue Evaluation per Investigator – target lesions	ITT set	Yes
	16.2.6.1.3	PCWG3 and LPC tumor assessment based on Radiological Soft Tissue Evaluation per Investigator – non-target lesions	ITT set	Yes

Header	Listing Number	Name	Analysis Set	Interim Analysis
	16.2.6.1.4	PCWG3 and LPC tumor assessment based on Radiological Soft Tissue Evaluation per Investigator – new lesions	ITT set	Yes
	16.2.6.1.5	PCWG3 Bone lesions based on Radiological Soft Tissue Evaluation per Investigator – new lesions	ITT set	Yes
	16.2.6.1.6	Clinical progression	ITT set	Yes
	16.2.6.1.7	Overall tumor response assessment based on PCWG3	ITT set	
	16.2.6.2	Prostate-specific antigen (PSA)	ITT set	Yes
		Exploratory Efficacy Endpoints		
	16.2.6.3.1	Overall iRECIST (central reading)tumor response assessment	ITT set	
	16.2.6.3.2	iRECIST (central reading) assessment – target lesions	ITT set	
	16.2.6.3.3	iRECIST (central reading) assessment – non-target lesions	ITT set	
	16.2.6.3.4	iRECIST (central reading) assessment – new lesions	ITT set	
	16.2.6.4.1	Duration of response based on PCWG3	ITT set	Yes
	16.2.6.4.2	Duration of response based iRECIST (central reading)	ITT set	
	16.2.6.4.3	Progression-free survival based on PCWG3	ITT set	Yes
	16.2.6.4.4	Progression-free survival based on iRECIST (central reading)	ITT set	
	16.2.6.4.5	Overall survival time	ITT set	
	16.2.6.4.6	Duration of response based on PCWG3	Cemi Mono on PD set	
	16.2.6.4.7	Duration of response based on iRECIST (central reading)	Cemi Mono on PD set	
	16.2.6.4.8	Progression-free survival based on PCWG3	Cemi Mono on PD set	
	16.2.6.4.9	Progression-free survival based on iRECIST (central reading)	Cemi Mono on PD set	
	16.2.6.4.10	Progression-free survival 2 based on PCWG3	Cemi Mono on PD set	
	16.2.6.5.1	Disease status reported during Survival Follow-up	ITT set	
		Pharmacodynamic and Biomarker Listings		
	16.2.6.6.1	Hormones (Testosterones [nmol/L])	Pharmacodynamic set	
	16.2.6.6.2	Cytokines	Pharmacodynamic set	
	16.2.6.6.3	HLA typing (optional)	Pharmacodynamic set	
	16.2.6.6.4	Tumor tissue sample (optional)	ITT set	
	16.2.6.6.5	TCR profiling (optional)	Pharmacodynamic set	

Header	Listing Number	Name	Analysis Set	Interim Analysis
	16.2.6.6.6	Genetics (optional)	Pharmacodynamic set	
16.2.7		Adverse Event Listings		
	16.2.7.1	Adverse Events	Safety set	Yes
	16.2.7.2	Cemiplimab treatment-emergent adverse events	Cemi Mono on PD set	
16.2.8		Listing of individual laboratory measurements by patient		
	16.2.8.1.1	Hematology	Safety set	
	16.2.8.1.2	Blood Chemistry	Safety set	
	16.2.8.1.3	Coagulation	Safety set	
	16.2.8.1.4	Urinalysis dipstick	Safety set	
	16.2.8.1.5	Urinalysis microscopic	Safety set	
	16.2.8.1.6	Thyroid hormones	Safety set	
	16.2.8.1.7	Serology	Safety set	
	16.2.8.1.8	Circulating tumor cells	Safety set	
	16.2.8.2	Other Safety Data	Safety set	
	16.2.8.2.1	Vital Signs	Safety set	
	16.2.8.2.2	12-lead ECG assessment	Safety set	
	16.2.8.2.3	Physical examination	Safety set	
	16.2.8.2.4	ECOG performance status	Safety set	

Note: no listing number should go beyond 16.2.8.x (i.e. 16.2.9)

